## **6.3 Treatment Period**

### **6.3.1 Day 1 (Baseline)**

Participants who meet all the inclusion and none of the exclusion criteria will be scheduled to return to the site for their Day 1 visit. This visit may be conducted over two consecutive days, as long as the dosing and PK samples are collected on the second day. The dosing day visit should be conducted in the morning, and the participant should be fasted (except for water, which is allowed) for approximately 8 hours prior to the visit.

At this visit the following will be performed:

- Confirm participant continues to meet eligibility criteria.
- Patient Global Assessment of disease severity (see Section 8.3).
- Record any new medical events since Screening, including SSc-specific signs and symptoms.
- Investigator assessment of the mRSS (see Section 8.3).
- Completion of the Scleroderma Health Assessment Questionnaire- Disability Index (SHAQ-DI) (see Section 8.3).
- Completion of the Scleroderma Clinical Trial Consortium Damage Index (SCTC-DI) (see Section 8.3).
- Completion of the 5-D Itch Scale (see Section 8.3).
- Symptom-directed physical examination (see Section 8.2).

- Weight.
- Measurement of vital signs pre-dose including blood pressure, heart rate, respiratory rate, and temperature (see Section 8.2).
- Spirometry assessment of FVC and FEV1 (see Section 8.3).
- Physician Global Assessment of disease severity (see Section 8.3).
- 12-lead ECG (see Section 8.2).
- Blood samples:
  - Pre-dose collection of blood samples for immune cell activation markers (see Section 8.4).
  - Pre-dose PK sample collected (see Section 8.1).
  - Pre-dose blood samples collected for cytokine and chemokine measurements (see Section 8.4).
  - Safety laboratory tests including haematology, biochemistry, coagulation, and urinalysis, and serum pregnancy test for WOCBP (see Section 8.2).
- Collect 2 x 3mm punch biopsy skin samples (see Section 8.4). For operational reasons, biopsies may be collected during the screening period once participants have been confirmed as eligible, as long as they are collected pre-dose.
- Review and record concomitant medications.

Eligible participants will be randomised, dispensed IMP, and will take their first dose of IMP at the study site, with the time of administration recorded.

- Participants will remain on site for PK blood samples to be collected at 1, 2, 3, 4, 5, 6, 7 and 8 hours post dose (see Section 8.1).
- Vital signs to be recorded immediately prior to 8-hour post-dose PK sample.
- Assess and record adverse events.

At the end of the visit participants will be reminded to take 2 capsules once daily for the duration of the trial Treatment Period.

### **6.3.2 Week 4 and Week 8**

There is a  $\pm 3$ -day window on each visit.

Participants should be contacted the day prior to their visit to remind them not to take their IMP on the morning of the visit until at site and instructed to do so by the study staff.

This visit should be conducted in the morning, and the participant should be fasted (except for water, which is allowed) for approximately 8 hours prior to the visit.

Participants will return to the site for the following assessments:

- Patient Global Assessment of disease severity (see Section 8.3).
- Record any SSc-specific signs and symptoms.
- Investigator assessment of the mRSS (see Section 8.3).

- Completion of the SHAQ-DI (see Section 8.3).
- Symptom-directed physical examination (see Section 8.2).
- Weight.
- Measurement of vital signs including blood pressure, heart rate, respiratory rate, and temperature (see Section 8.2).
- Spirometry assessment of FVC and FEV1 (see Section 8.3).
- Physician Global Assessment of disease severity (see Section 8.3).
- 12-lead ECG (see Section 8.2).
- Blood samples:
  - Pre-dose PK sample collected (see Section 8.1).
  - Pre-dose blood samples collected for cytokine and chemokine measurements (see Section 8.4).
  - Safety laboratory tests including haematology, biochemistry, coagulation, and urinalysis, and serum pregnancy test for WOCBP (see Section 8.2).
- Participants will take their dose of IMP at the study site, with the time of administration and that of the previous dose recorded.
- Review and record concomitant medications.
- Assess and record adverse events.
- Conduct IMP accountability and review compliance.
- Dispense new IMP bottle

### **6.3.3 Week 12 (End of Treatment) / Early Termination**

There is a  $\pm 3$ -day window on this visit.

Participants should be contacted the day prior to their visit to remind them not to take their IMP on the morning of the visit until at site and instructed to do so by the study staff.

This visit should be conducted in the morning, and the participant should be fasted (except for water, which is allowed) for approximately 8 hours prior to the visit.

At this visit the following will be performed:

- Patient Global Assessment of disease severity (see Section 8.3).
- Record any SSc-specific signs and symptoms.
- Investigator assessment of the mRSS (see Section 8.3).
- Completion of the SHAQ-DI (see Section 8.3).
- Completion of the SCTC-DI (see Section 8.3).
- Completion of the 5-D Itch Scale (see Section 8.3).
- Symptom-directed physical examination (see Section 8.2).

- Weight.
- Measurement of vital signs pre-dose including blood pressure, heart rate, respiratory rate, and temperature (see Section 8.2).
- Spirometry assessment of FVC and FEV1 (see Section 8.3).
- Physician Global Assessment of disease severity (see Section 8.3).
- 12-lead ECG (see Section 8.2).
- Blood samples:
  - Pre-dose collection of blood samples for immune cell activation markers (see Section 8.4).
  - Pre-dose PK sample collected (see Section 8.1).
  - Pre-dose blood samples collected for cytokine and chemokine measurements (see Section 8.4).
  - Safety laboratory tests including haematology, biochemistry, coagulation, and urinalysis, and serum pregnancy test for WOCBP (see Section 8.2).
- Collect 2 x 3mm punch biopsy skin samples (see Section 8.4).
- Review and record concomitant medications.
- Participants will take their dose of IMP at the study site, with the time of administration and that of the previous dose recorded.
  - Participants will remain on site for PK blood samples to be collected at 1, 2, 3, 4, 5, 6, 7 and 8 hours post dose (see Section 8.1).
  - Collection of blood samples for immune cell activation markers at 4 hours post dose (see Section 8.4).
  - Vital signs to be recorded immediately prior to 8-hour post-dose PK sample.
- Assess and record adverse events.
- Conduct IMP accountability and review compliance.

This is the end of the Treatment Period. The participant will not receive any IMP after this visit.

This visit should also be conducted as the final treatment visit in the case of early withdrawal/early termination of a participant.

#### **6.4 Week 16 (Follow up)**

There is a +1-week window on this visit. At this visit the following will be performed:

- Record any SSc-specific signs and symptoms.
- Investigator assessment of the mRSS (see Section 8.3).
- Symptom-directed physical examination (see Section 8.2).
- Weight.
- Measurement of vital signs including blood pressure, heart rate, respiratory rate, and temperature (see Section 8.2).

- 12-lead ECG (see Section 8.2).
- Safety laboratory tests including haematology, biochemistry, coagulation, and urinalysis, and serum pregnancy test for WOCBP (see Section 8.2).
- Review and record concomitant medications.
- Assess and record adverse events.

This is the final study visit.

## **7 TRIAL ENDPOINTS**

### **7.1 Primary Endpoints**

- FT011  $c_{max}$ ,  $t_{max}$ , and AUC in plasma after a single dose and after 12-weeks of treatment.
- Measurement of steady state FT011 levels in plasma.

Additional calculations may be performed, and metabolites may also be measured.

### **7.2 Secondary Endpoints**

#### **7.2.1 Safety Endpoints**

Safety will be assessed by:

- Treatment emergent adverse events from first dose of study drug to End of Study.
- Physical examination.
- Vital signs (blood pressure, heart rate, respiratory rate, and temperature).
- 12-lead ECG.
- Safety laboratory results (haematology, biochemistry, coagulation, and urinalysis).
- Use of concomitant medications.

#### **7.2.2 Efficacy Endpoints**

- Change in mRSS from Baseline at each visit.
- Change in percent predicted FVC from Baseline to Week 4, Week 8, and Week 12.
- Change in HAQ-DI Score from Baseline to Week 4, Week 8, and Week 12.
- Change in Patient Global Assessment Score from Baseline to Week 4, Week 8, and Week 12.
- Change in Physician Global Assessment Score from Baseline to Week 4, Week 8, and Week 12.
- The proportion of patients showing an improvement (defined as ACR Composite Response Index in Diffuse Cutaneous Systemic Sclerosis (CRISS) score predicted probability of  $\geq 0.60$ ) at Week 12.
- Change in the Scleroderma Clinical Trials Consortium Damage Index (SCTC-DI) score from Baseline to Week 12.
- Change in the 5-D Itch Scale from Baseline to Week 12.

### 7.3 Exploratory Endpoints

- [REDACTED]
- [REDACTED]
- [REDACTED]

## 8 TRIAL MEASUREMENTS

### 8.1 Pharmacokinetics

Details of the laboratory and sample collection, processing, storage, and shipment are described in the Laboratory Manual.

Blood samples for plasma PK analyses will be collected at the following time points:

- Day 1: within 30 minutes prior to IMP administration, and at 1, 2, 3, 4, 5, 6, 7 and 8 hours post dose.
- Week 4: within 30 minutes prior to IMP administration.
- Week 8: within 30 minutes prior to IMP administration.
- Week 12: within 30 minutes prior to IMP administration, and at 1, 2, 3, 4, 5, 6, 7 and 8 hours post dose.

A window of  $\pm 10$  minutes is allowed for all time points. Collections outside of these windows will be recorded as protocol deviations. Actual collection time must be recorded.

At each visit, the time of administration of the previous dose of IMP, and the time the dose is taken at the study site, must be recorded.

The PK samples will be shipped to a central laboratory for determination of the pharmacokinetics of FT011.

Metabolites may also be measured. Remaining samples will be stored for up to 10 years and may be used for additional research into FT011 or relevant indication biomarkers.

### 8.2 Safety and tolerability

Safety will be assessed by recording of AEs, laboratory parameters, vital signs, physical examination, and 12-lead ECG. Where multiple procedures are scheduled for the same nominal time point, safety blood samples should be taken after all other procedures have been performed.

- The physical examination will include the following: examination of general appearance, skin, head, neck (including thyroid), eyes, ears, nose, throat, heart, lungs, abdomen, lymph nodes, extremities, and nervous system. Height will be recorded at screening only. A symptom directed physical examination will be conducted at post-screening visits, based on signs and symptoms the patient has experienced or reported.

- Vital sign measurements should be taken after the participant has rested in a supine position for at least 5 minutes and include blood pressure (systolic and diastolic), heart rate (beats/minute), respiratory rate, and body temperature. The same arm (preferably the nondominant arm) and the appropriate size cuff should be used for each blood pressure measurement.
  - At the Day 1 and Week 12 visits, vital signs are to be recorded pre-dose and just prior to the 8-hour post dose PK sample.
- 12-lead ECGs will be performed. Participants should be in a resting supine position for 10 minutes prior to ECG collection. The Investigator (or a qualified observer at the investigational site) will interpret the ECG using one of the following categories: within normal limits, abnormal but not clinically significant, or abnormal and clinically significant. The heart rate from the ECG machine should not be used as part of the vital sign measurements.
- Blood and urine samples will be taken throughout the course of the study. On-study collections should be fasted. Details of the laboratory and sample collection, processing, storage, and shipment are described in the Laboratory Manual. The following specific tests will be performed at the study central laboratory:
  - Haematology: Haemoglobin, haematocrit, red blood cell count, red cell distribution width, mean corpuscular volume, mean corpuscular haemoglobin, mean corpuscular haemoglobin concentration, white blood cell count with differential, and platelet count.
  - Coagulation: Activated partial thromboplastin time, prothrombin time, international normalised ratio, fibrinogen.
  - Serum Chemistry: Sodium, potassium, magnesium, bicarbonate, phosphate, calcium, urea, urate, serum albumin, total protein, gamma-glutamyl transferase, alanine transaminase, aspartate transaminase, direct bilirubin, alkaline phosphatase, glucose, cholesterol, triglycerides, high-density lipoprotein, low-density lipoprotein, creatine phosphokinase, lactate dehydrogenase, and creatinine. The central laboratory will calculate and report the eGFR value.
  - Urinalysis: Mid-stream urine microscopy, culture and sensitivities, urinary albumin: creatinine ratio (ACR)
  - Serum pregnancy test: for women of childbearing potential.
- Participants will be questioned at each visit from Day 1 about any AEs they may have experienced since the previous visit. See Section 10.3 for further details on recording AEs.
- Participants will be questioned at each visit about any concomitant medications they may have taken since the previous visit. This will assist in identifying AEs.

### 8.3 Efficacy

- The mRSS is a validated physical evaluation of patient's skin thickness rated by clinical palpation using a 0-3 scale (0 = normal skin; 1 = mild thickness; 2 = moderate thickness; 3 = severe thickness with inability to pinch the skin into a fold for each of 17 surface anatomic areas of the body: face, anterior chest, abdomen, and, with right and left sides of the body separately evaluated, the fingers, forearms, upper arms, thighs, lower legs, dorsum of hands and feet. Individual values are summed and defined as the total skin score. Total score is 0 to 51 with higher scores indicating worse symptomology. Minimally clinically significant difference in MRSS is 3-5 points.

- Percent predicted FVC is calculated using equations incorporating age, gender, and race. It is calculated as  $(FVC \text{ Observed} / FVC \text{ predicted}) \times 100$ , where FVC predicted is calculated relative to a reference population. Forced expiratory manoeuvres will be performed at least in triplicate with the minimal requirement that three manoeuvres are "acceptable" and that two of these manoeuvres meet end-of-test and repeatability criteria for FVC and FEV1.
- The SHAQ-DI consists of 20 questions referring to eight component sets consisting of dressing/grooming, arising, eating, walking, hygiene, reach, grip, and activities. Each item is scored on a 4-point scale from 0 to 3: 0 = Without any difficulty; 1 = With some difficulty; 2 = With much difficulty; 3 = Unable to do. The eight scores of the eight sections are summed and divided by 8. If one section is not completed by a subject, the summed score is divided by 7. The total score indicates the patient's self-assessed level of disability - higher scores indicate worse symptomology. This outcome measure represents the change in mean score from baseline. A negative change from baseline indicates improvement. The Scleroderma HAQ (SHAQ) includes an additional five scleroderma-specific visual analogue scales (VAS), addressing overall disease activity, Raynaud's phenomenon, finger ulcers, breathing, and intestinal problems. A composite VAS score is not created nor are the individual VAS scores incorporated into the HAQ DI score.
- The Patient's Global Assessment represents the patient's overall assessment of current SSc status on a 100-mm horizontal VAS, ranging from 0 on the extreme left end of the scale indicating "extremely poor health", and 100 on the extreme right end indicating "excellent health".
- The Physician's Global Assessment is to be completed based on examination and overall assessment of the patient. The physician's assessment of the patient's SSc status will be scored on a 100-mm horizontal VAS, ranging from 0 on the extreme left end of the scale indicating "no disease activity" (symptom free), and 100 on the extreme right end indicating "worst imaginable disease activity".
- The ACR CRISS was developed using expert consensus and data driven approaches for use in clinical trials. The exponential algorithm determines the predicted probability of improvement from baseline, incorporating change in the mRSS, FVC percent predicted, physician and patient global assessments, and HAQ-DI. The outcome is a continuous variable between 0.0 and 1.0 (0 - 100%). A higher score indicates greater improvement.

The application of CRISS algorithm in a randomised clinical trial is a 2-step process.

In the first step, participants will be clinically evaluated to determine whether the participant has improved or not. A participant is considered not improved and is assigned a probability score of improving equal to 0.0, irrespective of improvement on other core items, if he/she develops:

1. New scleroderma renal crisis.
2. Decline in FVC % predicted  $\geq 15\%$  (relative), confirmed by another FVC % within a month, high resolution computed tomography (HRCT) to confirm interstitial lung disease (if previous HRCT did not show interstitial lung disease) and FVC % predicted below 80% predicted (attributable to SSc).
3. New onset of left ventricular failure (defined as ejection fraction  $\leq 45\%$ ) or new onset of pulmonary arterial hypertension requiring treatment (attributable to SSc).

If the participant is determined to exhibit improvement in the first step (i.e., not assigned a 0.0), the second step involves computing the predicted probability of improving (a score between 0.0 and 1.0, inclusive) using the equation:

$$\frac{\exp[-5.54 - 0.81 \cdot \Delta MRSS + 0.21 \cdot \Delta FVC\% - 0.40 \cdot \Delta Pt-glob - 0.44 \cdot \Delta MD-glob - 3.41 \cdot \Delta HAQ-DI]}{1 + \exp[-5.54 - 0.81 \cdot \Delta MRSS + 0.21 \cdot \Delta FVC\% - 0.40 \cdot \Delta Pt-glob - 0.44 \cdot \Delta MD-glob - 3.41 \cdot \Delta HAQ-DI]}$$

where  $\Delta MRSS$  indicates the change in mRSS from baseline to the visit,  $\Delta FVC$  denotes the change in FVC % predicted from baseline to the visit,  $\Delta Pt-glob$  indicates the change in patient global assessment,  $\Delta MD-glob$  denotes the change in physician global assessment, and  $\Delta HAQ-DI$  is the change in HAQ-DI. Note that all changes are absolute changes.

Participants for which the predicted probability is greater or equal to 0.60 are considered improved, while participants for which the predicted probability is below 0.60 are considered not improved.

- The SCTC-DI is a 23-item composite damage index to quantify organ damage in systemic sclerosis.
- The 5-D itch scale is a validated brief multidimensional questionnaire designed to be useful as an outcome measure in clinical trials. The five dimensions are degree, duration, direction, disability, and distribution.

#### 8.4 Exploratory

[REDACTED]

- [REDACTED]

- [REDACTED]

- [REDACTED]

[REDACTED]

## **9 STUDY OVERSIGHT**

### **9.1 Data Safety Monitoring Board**

An independent DSMB will be established prior to recruitment start, with appropriate charter that defines its roles and responsibilities. The DSMB will monitor accruing trial safety results and PK data at intervals throughout the study. The main purpose of the DSMB will be to protect the interests of the participants included in the trial.

The charter will specify the intervals for formal DSMB meetings.

The DSMB will convey to Certa Therapeutics their recommendations as to whether the trial may continue as planned or if the trial should be modified or stopped. The final decision on whether the study should be modified or stopped will be the responsibility of Certa Therapeutics. Any decision to modify or stop will be communicated to investigators and regulatory authorities (RA) by Certa Therapeutics (or their representatives). The DSMB may also report PK data in a blinded fashion.

The DSMB will also review any serious adverse events (SAE) that occur during the study.

Certa Therapeutics may also decide to cease enrolment at any time if unfavourable safety data lead to the conclusion that the benefit-risk assessment for the trial is no longer positive.

## **10 ADVERSE EVENTS**

The definitions of AEs and SAEs are given below. It is extremely important that all staff involved in the trial are familiar with the content of this section. The PI is responsible for ensuring this.

AEs and SAEs will be captured from the time of the first dose of IMP through to the final study visit.

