## 1 PROTOCOL SYNOPSIS

Study Title:	A phase II, randomised, double blind, placebo-controlled study of the pharmacokinetics, pharmacodynamic effects, and safety, of oral FT011 in participants with diffuse systemic sclerosis
Study Period:	2021 - 2022
Objectives:	
Primary objective:
 

To assess the pharmacokinetics (PK) of oral FT011 in participants with diffuse systemic sclerosis (SSc).

 
Secondary objectives:
 

To assess the safety and tolerability of oral FT011 compared to placebo in participants with diffuse SSc.

To evaluate the short-term efficacy of oral FT011 compared to placebo in improving disease activity in participants with diffuse SSc.

 
[REDACTED]
 

[REDACTED]

 

[REDACTED]

 

[REDACTED]

Number of participants:	Approximately 30 participants will be randomised and treated.
Study design	
This is a multi-centre, randomised, double blind, placebo-controlled study to assess the pharmacokinetic pharmacodynamic effects and safety of FT011 in participants with diffuse systemic sclerosis.
 
The targeted study population is patients with diffuse SSc with a disease duration of ≤10 years from onset of first non-Raynauds symptom, and a modified Rodnan Skin Score (mRSS) of 15 to 40 at the screening visit. Patients meeting all eligibility criteria will have a baseline skin biopsy (2 x 3mm punch biopsies) taken before being randomised 1:1:1 to FT011 200mg, FT011 400mg, or placebo.
 
Participants will take their investigational medicinal product (IMP) once a day for 3 months (12 weeks), in addition to their standard-of-care scleroderma medications. They will return to the site for study visits at Weeks 4, 8, and 12. Week 12 is the end of the study Treatment Period. A final study follow-up visit will be conducted one month after they complete treatment (Week 16).

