Skin punch biopsies (two pre-dose)		X 			X	
Prior and Concomitant Medication	X	X	X	X	X	X
Adverse Events		X	X	X	X	X
Randomisation		X				
Dispense IP		X	X	X		
IMP accountability			X	X	X	
IMP administration		← X →				

 Baseline (Day 1) biopsies may be collected at any time pre-dose once the participant has been confirmed as eligible, including on a different day.

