#### **5.4.5 Concomitant Medications and Treatments**

Methotrexate must not be taken within the 2 weeks prior to Day 1, or during the study.

Participants should be maintained on their current SSc medications during the Treatment Period, unless they have a mRSS increase from Baseline of 5 or more. In this case they may start immunosuppressive medications, or, if already taking those, have their immunosuppressive medications or doses changed.

The following medications are exclusionary if taken during the specified pre-study period and should not be taken during the study treatment period.

- Other anti-fibrotic agents including D-penicillamine or tyrosine kinase inhibitors (nilotinib, imatinib, dasatinib) in the month prior to Screening.
- Biologic drugs such as TNF inhibitors, tocilizumab, or JAK inhibitors, in the 3 months prior to Screening.
- Rituximab in the 6 months prior to Screening.
- Cyclophosphamide oral or IV in the 3 months prior to Screening.
- Oral prednisolone >10 mg per day or IV steroids in the month prior to Screening.

[REDACTED]

If these medications are required to be used during the study Treatment Period, the investigator should discuss with the Medical Monitor whether the participant may remain on study or must be withdrawn.

Any treatment or medication that is used, other than the IMP, must be noted in the source documentation and the Case Report Form (CRF). This record should include the drug name, the dose and frequency, route of administration, the start and stop date of administration, and the indication.

Medications or treatments taken in the 1 month prior to Baseline will be recorded on the prior medication CRF. Any use of medications for the treatment of AE will be recorded on the concomitant medication CRF.

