### **10.3 Eliciting and Recording of Adverse Events**

At every study visit, participants must be asked a standard, non-directed question, such as, “How have you been feeling since your last visit?” to elicit any medically related changes in their well-being. They may also be asked if they have been hospitalised, had any accidents, used any new medications, or changed concomitant medication regimens (including prescription drugs, over-the-counter medications, vitamins, herbal products, and minerals). Responses must be documented in the source documents.

In addition to patient observations, AEs must be documented for any clinically significant diagnosis resulting from abnormal laboratory test values, physical examination findings, or ECG abnormalities, or from other documents that are relevant to participant safety.

AEs will be captured from the time of first IMP dose, until the final study visit. Conditions occurring prior to the first dose of IMP will be recorded as medical history. SAEs judged to be possibly related to FT011 occurring to a study participant after the SAE reporting period will be reported to the sponsor if the Investigator becomes aware of them.

It is preferable that AEs are reported as diagnoses if one can be made, rather than individual signs and symptoms. The AE description, start and stop dates, intensity, causality, and outcome must be recorded, as well as any actions taken.

Unless a diagnosis is made, or signs and symptoms are present, abnormal laboratory values, physical examination findings, abnormal vital signs, or ECG abnormalities, should only be reported as AEs if they cause the participant to discontinue from the trial, the investigator feels it is clinically significant, or they meet a criterion for a SAE.

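### Events that start before the first dose, including serious ones caused by the required baseline biopsies, are recorded only as medical history, with no AE or SAE status

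*Protocol*

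**What the plan says.** Protocol Section 10 sets the capture window: "AEs and SAEs will be captured from the time of the first dose of IMP through to the final study visit". Section 10.3 repeats the starting point and says what happens to earlier events: "Conditions occurring prior to the first dose of IMP will be recorded as medical history". Neither section makes an exception for events that are serious or that result from a study procedure. Section 10.3 does provide for the other end of the window: a late SAE thought possibly related to FT011 still goes to the sponsor if the investigator learns of it.

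The trial asks things of participants before that window opens. Section 5.1 places the two 3 mm punch biopsies before randomisation. A footnote to the schedule in Section 2 states: "Baseline (Day 1) biopsies may be collected at any time pre-dose once the participant has been confirmed as eligible, including on a different day". Section 6.3.1 confirms that "biopsies may be collected during the screening period once participants have been confirmed as eligible". Section 5.4.5 adds: "Methotrexate must not be taken within the 2 weeks prior to Day 1, or during the study". Section 6.2 allows up to 28 days for screening.

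The 24-hour report to the sponsor (Section 10.4.1) applies to SAEs whatever their cause. Follow-up to resolution or stabilisation (Section 10.5) applies to AEs and SAEs.

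**The concern.** A biopsy done for research, or a drug stopped in order to enter a trial, can harm a participant before any IMP is taken. Under the rule as written, such an event is not an AE, so it cannot be an SAE however serious it is. The same biopsy procedure at Week 12 (Section 6.3.3) falls inside the window. At stake is participant safety during screening: whether a serious event caused by the research is reported promptly, followed up, and put before those who oversee safety. No efficacy estimate or treatment-emergent AE table depends on it.

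**Working it through.** The plan gives no figure to reproduce, so the check follows one event through the text and then looks at its likely size.

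**1. What can happen before the window opens.** The baseline biopsies are always pre-dose and may fall on an earlier day. The methotrexate-free period is 14 days and screening lasts up to 28 days. Since 14 is less than 28, that period can lie wholly after consent.

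**2. How one event is handled.** Take an inpatient admission that results from a biopsy and begins before the first dose.

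| Question | Starts before first dose | Starts after first dose |
|---|---|---|
| Recorded as | Medical history (10.3) | AE, and SAE under 10.2 |
| 24-hour report (10.4.1) | Not triggered by the text | Required |
| Follow-up (10.5) | Not triggered by the text | Required |
| AE summaries (SAP 15.1) | No | Yes |

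**3. Where the pre-dose record goes.**
- Sponsor: Section 6.3.1 has new medical events since Screening recorded at Day 1, and Section 11.1 puts study data into the EDC. SAP Section 11 codes, summarises and lists medical history. The sponsor therefore receives the event, but as medical history and with no reporting clock.
- DSMB: SAP Section 4.1 and Appendix 3 list AEs, SAEs and disease history. They name no general medical history output.
- Participants biopsied but never dosed: Section 5.4.9 foresees withdrawal between randomisation and dosing. SAP Section 11 presents medical history for the Safety Analysis Set, which requires a dose. SAP Section 6 bases listings on all who consented. Such a participant's event therefore appears in listings at most.

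**4. Passages that pull the other way.**
- Protocol 9.1 has the DSMB review SAEs arising at any time in the study, without tying this to the first dose.
- Protocol 10.1 gives an AE before the first FT011 dose as an example of an event that is not related.
- Protocol 8.2 has participants asked at Day 1 about AEs since the previous visit, which is Screening.
- SAP 15.1 includes AEs that are not treatment-emergent in the overall listing.

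All four presuppose, or leave room for, AEs that start before the first dose. Sections 10 and 10.3 say that these are not captured. In addition, the causality scale in Section 10.1 rates events against the IMP only and has no category for study procedures.

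**5. Size.** The synopsis gives the number of participants: "Approximately 30 participants will be randomised and treated". The documents give no rate for pre-dose events, so the rate p below is an assumption. Expected events = 30 × p, and the chance of at least one = 1 − (1 − p)^30.

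| Assumed p | Expected events | Chance of at least one |
|---|---|---|
| 1% | 0.3 | 26% |
| 3% | 0.9 | 60% |
| 5% | 1.5 | 79% |
| 10% | 3.0 | 96% |

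Here p covers any event from a biopsy or from stopping methotrexate that starts before the first dose, serious or not. Serious events would be rarer.

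**The case against.** The best defence is that capture from first dose is a declared choice. It fits the AE definition in Section 10.1, which refers to a participant who has been given a product, and it changes no treatment-emergent or efficacy result. That is correct, and it is why this is an improvement and not an error in the analysis.

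A reader might infer more than the documents support:

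- **That pre-dose harm reaches neither the sponsor nor the DSMB.** Step 3 shows that the sponsor does receive it. For the DSMB, the absence is inferred from an output list. Section 9.1 gives a wider remit, and the charter, which SAP 4.1 says describes the analyses more fully, is not among the documents.
- **That half of all biopsies, or 4 of 20 study weeks, lie outside capture.** With 30 participants, 30 × 2 = 60 of 30 × 4 = 120 punches do precede the first dose. But capture depends on when an event starts, not on when the punch is taken. After a Day 1 biopsy, a complication that begins after the dose is an AE. Under the synopsis and SAP 15.1, one that worsens after the dose is treatment-emergent. Four weeks is the maximum screening length, and biopsies must wait until eligibility is confirmed.
- **That the protocol prescribes a methotrexate wash-out.** It sets a 2-week exclusion. Participants may have stopped before consent, and the number affected is unknown and may be zero.

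Two further limits apply. Section 8.4, to which the biopsy steps refer, and Section 3.6 on risk and benefit are redacted, so handling specific to biopsies could be stated there. Sites must also report SAEs to their ethics committee (Section 13.8), though that duty too depends on an event being called an SAE.

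**Conclusion.** The point holds in a limited form. In the visible text, an event that starts before the first dose is medical history even if it is serious and caused by a required study procedure. It therefore lacks AE or SAE status, the 24-hour report and AE follow-up. The sponsor still sees it in the data. The DSMB output list does not show it, and for a participant never dosed it appears in listings at most. The rule also conflicts with Protocol 9.1 and 10.1 and SAP 15.1, so a site cannot tell from the text how to handle a serious pre-dose event.

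This is a low-cost safety improvement. Its size cannot be fixed from the documents; the 0.3 to 3 expected events rest wholly on the assumed 1% to 10%. The conclusion also assumes that neither the redacted sections nor the DSMB charter already supplies a route.

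**What to change.** 1. Amend Protocol Sections 10 and 10.3 so that SAEs are captured from informed consent, and AEs related to study procedures from the first study procedure.
2. Align the AE row of the schedule, and reconcile both sections with Protocol 9.1 and 10.1 and SAP 15.1. State explicitly that a serious pre-dose event follows the 24-hour route in Section 10.4.1.
3. Keep the treatment-emergent definition at the first dose. SAP 15.1 already limits AE summaries to treatment-emergent events and already lists the others, so no summary table changes.
4. List pre-dose events for everyone who consented, including those biopsied but never dosed.

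The cost is a few lines of protocol text, minor CRF changes and a few more pre-dose records. The SAP is dated 16 November 2022 and Protocol 13.7 proposed completion in the third quarter of 2022, so conduct may already be over. In that case step 4 can still be done alone, by listing medical-history entries with onset after consent.
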